**Stable Disease (SD)**

Neither sufficient shrinkage to qualify for PR nor sufficient increase to qualify for PD, taking as reference the smallest sum diameters while on study

b. Evaluation of Non-Target Lesions

**Complete Response (CR)**

Disappearance of all non-target lesions and normalization of tumor marker level. All lymph nodes must be non-pathological in size (<10 mm short axis)

Note: If tumor markers are initially above the upper normal limit, they must normalize for a patient to be considered in complete clinical response.

**Non-CR/Non-PD (Stable Disease, SD)**

Persistence of one or more non-target lesion(s) and/or maintenance of tumor marker level above the normal limits.

**Progressive Disease (PD)**

Appearance of one or more new lesions and/or *unequivocal progression* of existing non-target lesions. *Unequivocal progression* should not normally trump target lesion status. It must be representative of overall disease status change, not a single lesion increase.

Although a clear progression of “non-target” lesions only is exceptional, the opinion of the treating physician should prevail in such circumstances, and the progression status should be confirmed at a later time by the review panel (or Principal Investigator).

c. Evaluation of Best Overall Response

The best overall response is the best response recorded from the start of the treatment until disease progression/recurrence (taking as reference for progressive disease the smallest measurements recorded since the treatment started). The patient's best response assignment will depend on the achievement of both measurement and confirmation criteria.

Target Lesions	Non-Target Lesions	New Lesions	Overall Response	Best Overall Response when Confirmation is Required*
CR	CR	No	CR	≥4 wks. Confirmation**
CR	Non-CR Non-PD	No	PR	≥4 wks. Confirmation**
CR	Not evaluated	No	PR	
PR	Non-CR Non-PD Not evaluated	No	PR	
SD	Non-CR Non-PD Not evaluated	No	SD	Documented at least once ≥4 wks. from baseline**

Target Lesions	Non-Target Lesions	New Lesions	Overall Response	Best Overall Response when Confirmation is Required*
PD	Any	Yes or No	PD	No prior SD, PR or CR
Any	PD***	Yes or No	PD	
Any	Any	Yes	PD	

*See RECIST 1.1 manuscript for further details on what is evidence of a new lesion.  **Only for non-randomized trials with response as primary endpoint.  ***In exceptional circumstances, unequivocal progression in non-target lesions may be accepted as disease progression
				

- d. Patients with a global deterioration of health status requiring discontinuation of treatment without objective evidence of disease progression at that time should be reported as “*symptomatic deterioration.*” Every effort should be made to document the objective progression even after discontinuation of treatment.
- e. In some circumstances, it may be difficult to distinguish residual disease from normal tissue. When the evaluation of complete response depends on this determination, it is recommended that the residual lesions be investigated (fine needle aspirate/biopsy) before confirming the complete response status.

### **6.5.2 Confirmatory Measurement/Duration of Response**

- Confirmation

To be assigned a status of PR or CR, changes in tumor measurements must be confirmed by repeat assessments that should be performed at least 4 weeks after the criteria for response are first met.

- Duration of Overall Response

The duration of overall response is measured from the time measurement criteria are met for CR or PR (whichever is first recorded) until the first date that recurrent or progressive disease is objectively documented (taking as reference for progressive disease the smallest measurements recorded since the treatment started).

The duration of overall CR is measured from the time measurement criteria are first met for CR until the first date that progressive disease is objectively documented.

### **6.5.3 Measurable Disease**

Measurable lesions are defined as those that can be accurately measured in at least one dimension (longest diameter to be recorded) as:

- By chest x-ray:  $\geq 20$  mm;
- By CT scan:
  - Scan slice thickness 5 mm or under as  $\geq 10$  mm with CT scan
  - Scan slice thickness  $> 5$  mm: double the slice thickness
- With calipers on clinical exam:  $\geq 10$  mm.

All tumor measurements must be recorded in millimeters (or decimal fractions of centimeters).

Note: Tumor lesions that are situated in a previously irradiated area might or might not be considered measurable. *If the investigator thinks it appropriate to include them, the conditions under which such lesions should be considered must be defined in the protocol.*

#### **6.5.4 Malignant Lymph Nodes**

To be considered pathologically enlarged and measurable, a lymph node must be  $\geq 15$  mm in short axis when assessed by CT scan (CT scan slice thickness recommended to be no greater than 5 mm). At baseline and in follow-up, only the short axis will be measured and followed.

#### **6.5.5 Non-Measurable Disease**

All other lesions (or sites of disease), including small lesions (longest diameter  $< 10$  mm or pathological lymph nodes with  $\geq 10$  to  $< 15$  mm short axis), are considered non-measurable disease. Bone lesions, leptomeningeal disease, ascites, pleural/pericardial effusions, lymphangitis cutis/pulmonitis, inflammatory breast disease, and abdominal masses (not followed by CT or MRI), are considered as non-measurable.

Note: Cystic lesions that meet the criteria for radiographically defined simple cysts should not be considered as malignant lesions (neither measurable nor non-measurable) since they are, by definition, simple cysts.

‘Cystic lesions’ thought to represent cystic metastases can be considered as measurable lesions, if they meet the definition of measurability described above. However, if non-cystic lesions are present in the same patient, these are preferred for selection as target lesions.

#### **6.5.6 Target Lesions**

All measurable lesions up to a maximum of 2 lesions per organ and 5 lesions in total, representative of all involved organs, should be identified as **target lesions** and recorded and measured at baseline. Target lesions should be selected on the basis of their size (lesions with the longest diameter), be representative of all involved organs, but in addition should be those that lend themselves to reproducible repeated measurements. It may be the case that, on occasion, the largest lesion does not lend itself to reproducible measurement in which circumstance the next largest lesion which can be measured reproducibly should be selected. A sum of the diameters (longest for non-nodal lesions, short axis for nodal lesions) for all target lesions will be calculated and reported as the baseline sum diameters. If lymph nodes are to be included in the sum, then only the short axis is added into the sum. The baseline sum diameters will be used as reference to further characterize any objective tumor regression in the measurable dimension of the disease.

Progressive disease by RECIST criteria [1] noted after the first re-staging scan may represent disease that was not detected on the pre-study scan, and a confirmatory scan will be required at the next scheduled re-staging evaluation unless clinically not indicated. If confirmed, progression should be dated by the initial time when the lesions are first detected. If progressive disease by RECIST criteria is seen after cycle 2, but not confirmed on subsequent restaging scan, the scans from after cycle 2 would serve as the baseline scan to evaluate for disease progression .

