##### **Progressive Disease (PD)**

At least a 20% increase in the sum of the diameters of target lesions, taking as reference the smallest sum on study (this includes the baseline sum if that is the smallest on study). In addition to the relative increase of 20%, the sum must also demonstrate an absolute increase

of at least 5 mm. (Note: the appearance of one or more new lesions is also considered progressions)

Note: determination of PD will not be made prior to the Day 60 evaluation.

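### Sections 6.5.6 and 6.5.8 contradict the RECIST 1.1 definition of progression in 6.5.1.1, and 8.1 does not say which rule defines progression for time to progression and 6-month PFS

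*Combined protocol and SAP*

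**What the plan says.** Section 6.5 declares RECIST 1.1 for response and progression. Section 6.5.1.1 requires a rise of at least 20% and 5 mm in the target-lesion sum, "taking as reference the smallest sum on study (this includes the baseline sum if that is the smallest on study", and also counts new lesions. Its non-target criteria open with "Appearance of one or more new lesions and/or". No confirmatory scan is asked for. The one later check concerns progression in non-target lesions only, where "the progression status should be confirmed at a later time by the review panel" or the Principal Investigator. The best-overall-response text in 6.5.1.1(c) and the duration rule in 6.5.2 likewise take the smallest measurement since treatment began as the reference.

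Section 6.5.6 then says that RECIST progression at the first restaging "may represent disease that was not detected on the pre-study scan", and that "a confirmatory scan will be required at the next scheduled re-staging evaluation unless clinically not indicated". It adds: "If confirmed, progression should be dated by the initial time when the lesions are first detected". If progression seen after cycle 2 is not confirmed, "the scans from after cycle 2 would serve as the baseline scan to evaluate for disease progression". Section 6.5.8 sets a minimum of two new lesions on bone scan, with the same confirmation and re-baselining. Both sections cite reference 84, a guideline for prostate-cancer trials.

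Section 8.1 uses disease progression as an event for time to progression and plans a 6-month PFS probability. It gives no definition of progression and no cross-reference.

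**The concern.** The same scans can give two answers. A first-restaging scan that meets 6.5.1.1 is an event on that date. Under 6.5.6 it is no event if the next restaging does not confirm it, and the reference for later progression is reset. Nothing ranks the two rules. In an open, single-arm trial with 7 to 21 evaluable patients per cohort, the choice could be made after the scans are known, and one patient is a visible share of the estimate.

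The added text also fits this trial poorly. Section 2.1.1.1 does not list prostate cancer. Sections 3.1 and 3.5.2 and Appendix 2 restage after each three-cycle course, so no scan is scheduled after cycle 2. The label is probably left over from the 28-day regimen in 1.3.4, which was assessed after two cycles. The stated reason, disease missed at baseline, suits new lesions but not growth of target lesions already measured at baseline; the rule covers both.

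**Working it through.** **1. The plan's own figure.** Section 8 gives 70% early termination under a 5% response rate: 0.95^7 = 0.698. The full rule (stop at 0 of 7; success at 3 or more of 21) has type I error 0.064 and power 0.904 at a 30% response rate, within the stated 0.10 limits. No progression rule enters these figures.

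**2. The rules side by side.**

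| Item | 6.5.1.1 and 6.5.2 | 6.5.6 and 6.5.8 |
|---|---|---|
| Confirmatory scan | None | Next restaging, unless not clinically indicated |
| Reference | Smallest since treatment began | Reset to the after-cycle-2 scan if unconfirmed |
| New bone lesions | One is enough | Two needed on bone scan |
| Date of confirmed progression | First scan meeting the criteria | First detection (same date) |

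The date of confirmed progression agrees; the other three items do not. The bone rule is largely latent: 2.2, 3.5.2 and 3.5.4 name no bone scan, so one would occur only as other standard imaging.

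**3. Timing.** Inputs: 21-day cycles with a window of +7/-3 days (3.2), and restaging 14 days (+12/-3) after each three-cycle course (3.1; Appendix 2, footnote e), that is, 11 to 26 days after course end. Days run from first infusion, with no gap between courses.
- First restaging: 63 + 11 = 74 to 63 + 26 = 89.
- Second: 126 + 11 = 137 to 126 + 26 = 152.
- Third: 189 + 11 = 200 to 189 + 26 = 215.
- Six months: 365.25/2 = 183 days.

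Unconfirmed progression at the first restaging is therefore an event before six months under 6.5.1.1. Under 6.5.6 the second restaging has by definition not confirmed it, and the next scheduled scan that could show progression is the third, after day 183. If all nine cycles last 18 days, the third can fall at 162 + 11 = day 173, so six-month status need not always change. If the first three cycles last 28 days, the first restaging is at 84 + 26 = day 110 at the latest, still before six months. Section 8.1 counts from enrollment, which is no later than first infusion, so the third restaging is no earlier on that clock. A gap between courses makes it later.

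**4. Reference sum.** Let the smallest sum be 100 mm. Progression under 6.5.1.1 starts at 100 x 1.20 = 120 mm, so a first restaging of 125 mm meets it. If the second sum is below 120 mm, progression is unconfirmed. With the first restaging as the new baseline and the smallest-sum rule still running, the reference becomes that second sum, so the next threshold is below 120 x 1.20 = 144 mm. A second sum of 105 mm gives 105 x 1.20 = 126 mm. A later sum of 122 mm is then progression against 100 mm (+22%) but not against 105 mm (17/105 = +16%).

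**5. Size per patient.** Without censoring before six months, the estimate is a simple proportion. One reclassified patient moves it by 1/21 = 4.8 points in a full cohort, or 1/7 = 14.3 points in a cohort stopped at stage 1.

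**The case against.** The best defence is that the rules are layered. Section 6.5.6 starts from RECIST progression and adds confirmation, much as 6.5.2 adds confirmation to response. A specific rule under the same heading can qualify a general one. This makes the confirmation step intelligible. It does not reconcile a reset baseline with the smallest-measurement reference in 6.5.1.1(c) and 6.5.2, or two bone lesions with one. It does not supply a scan after cycle 2, and it does not tell the analyst which rule 8.1 uses.

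A reader might infer that confirmation is incompatible with trial conduct. The Précis and 3.6.2 remove patients at progression, 3.4 requires stable or responding disease for another course, and 3.5.4 schedules follow-up scans only for such patients. The documents do not support that in full, because 6.5.6 waives the scan where it is not clinically indicated, so a patient can be removed without one. What remains unclear is whether a patient awaiting a confirmatory scan may continue treatment.

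A reader might also infer that the first restaging can precede the point set by "determination of PD will not be made prior to the Day 60 evaluation". Counting from the last infusion with 18-day cycles gives 2 x 18 + 7 + 11 = day 54. But 3.1 and Appendix 2 count from the end of the course, which gives day 74, or 54 + 11 = day 65 with 18-day cycles. Both are after Day 60.

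Finally, time to progression and PFS are not among the objectives in 1.1 or the endpoints in 8.3. They are descriptive, which limits the weight of the point.

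**Conclusion.** The contradiction is real and 8.1 leaves it open. It affects progression at the first restaging that is not confirmed and, if a bone scan is done, a single new bone lesion. Each such patient can shift 6-month PFS by 4.8 or 14.3 points. This assumes no censoring, no unscheduled scan, that the after-cycle-2 scan means the first restaging, and that the patient continues on study to later restagings. The number of such patients cannot be derived from the documents.

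Two stronger readings should not be drawn. First, a reader might take the re-baselined threshold as 125 x 1.20 = 150 mm, or as at least 1.20 x 1.20 = 1.44 times the smallest sum. That requires the smallest-sum rule to be switched off after re-baselining and the lower second scan to be ignored, and no text says so. Second, a reader might infer that the Simon decision rules are compromised. Progression does close the window for best response, so a response after unconfirmed progression would be ambiguous. However, the documents give no basis for expecting or sizing this, and the design figures do not depend on it.

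**What to change.** State in 8.1 that progression for all endpoint analyses is RECIST 1.1 as in 6.5.1.1, dated at the first scan that meets it. The panel or Principal Investigator check for non-target-only progression can stay. Delete the confirmation and re-baselining text in 6.5.6 and 6.5.8 and the two-bone-lesion rule, or limit them to treatment decisions. Where text is kept, replace cycle 2 with first restaging. Say in 3.4 and 3.6.2 whether a patient awaiting a confirmatory scan may continue. The Day 60 note needs no change.

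The cost is a few sentences and no new scans. The downside is that an occasional lesion missed at baseline will count as progression, so time to progression may be slightly shorter.

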#### **6.5.7 Non-Target Lesions**

All other lesions (or sites of disease) including any measurable lesions over and above the 5 target lesions should be identified as **non-target lesions** and should also be recorded at baseline.

Measurements of these lesions are not required, but the presence, absence, or in rare cases unequivocal progression of each should be noted throughout follow-up.

#### **6.5.8 Metastatic Bone Lesions**

Disease progression is considered if a minimum of two new lesions is observed on bone scan. New lesions seen by the end of cycle 2 or before cycle 3 (with the first re-staging bone scan) may represent disease that was not detected on the pre-study scan, and a confirmatory scan will be required at the next scheduled re-staging bone scan unless clinically not indicated. If confirmed, progression should be dated by the initial time when the lesions are first detected. If new lesions are seen after cycle 2, but no additional lesions are seen on confirmatory scans, the scans from post-cycle 2 would serve as the baseline scan to evaluate for disease progression .

#### **6.5.9 Clinical Lesions**

Clinical lesions will only be considered measurable when they are superficial (e.g., skin nodules and palpable lymph nodes) and  $\geq 10$  mm diameter as assessed using calipers (e.g., skin nodules). In the case of skin lesions, documentation by color photography, including a ruler to estimate the size of the lesion, is recommended.

#### **6.5.10 Guidelines for Evaluation of Measurable Disease**

All measurements should be taken and recorded in metric notation using a ruler or calipers. All baseline evaluations should be performed as closely as possible to the beginning of treatment and never more than 4 weeks before the beginning of the treatment.

The same method of assessment and the same technique should be used to characterize each identified and reported lesion at baseline and during follow-up. Imaging-based evaluation is preferred to evaluation by clinical examination unless the lesion(s) being followed cannot be imaged but are assessable by clinical exam.

#### **6.5.11 Methods of Measurement**

Chest X-ray - Lesions on chest x-ray are acceptable as measurable lesions when they are clearly defined and surrounded by aerated lung. However, CT is preferable.

CT and MRI - CT and MRI are the best currently available and reproducible methods to measure target lesions selected for response assessment. For this study helical Multi-detector CT will be performed with cuts of 5 mm in slice thickness for chest, abdomen and pelvis lesions and 2-3 mm thickness for head and neck lesions.

#### **6.5.12 Additional response evaluation using volumetric analysis**

In addition, the utility of volumetric tumor measurement in patients with measurable disease will be prospectively evaluated and compared to 1D and 2D measurements.

### **6.6 TOXICITY CRITERIA:**

The following adverse event management guidelines are intended to ensure the safety of each patient while on the study. The descriptions and grading scales found in the revised NCI Common Terminology Criteria for Adverse Events (CTCAE) version 4.0 will be utilized for AE reporting. All appropriate treatment areas have access to a copy of the CTCAE version 4.0. A copy of the CTCAE version 4.0 can be downloaded from the CTEP web site (<http://ctep.cancer.gov>).

## **7 SAFETY REPORTING REQUIREMENTS/DATA AND SAFETY MONITORING PLAN**

### **7.1 ADVERSE EVENT DEFINITIONS**

#### **7.1.1 Adverse Event**

An adverse event is any untoward medical occurrence in a human subject, including any abnormal sign (for example, abnormal physical exam or laboratory finding), symptom, or disease, temporally associated with the subject's participation in research, whether or not considered related to the subject's participation in the research

#### **7.1.2 Suspected adverse reaction**

Suspected adverse reaction means any adverse event for which there is a reasonable possibility that the drug caused the adverse event. For the purposes of IND safety reporting, 'reasonable possibility' means there is evidence to suggest a causal relationship between the drug and the adverse event. A suspected adverse reaction implies a lesser degree of certainty about causality than adverse reaction, which means any adverse event caused by a drug.

#### **7.1.3 Unexpected adverse reaction**

An adverse event or suspected adverse reaction is considered "unexpected" if it is not listed in the investigator brochure or is not listed at the specificity or severity that has been observed; or, if an investigator brochure is not required or available, is not consistent with the risk information described in the general investigational plan or elsewhere in the current application. "Unexpected" also refers to adverse events or suspected adverse reactions that are mentioned in the investigator brochure as occurring with a class of drugs or as anticipated from the pharmacological properties of the drug, but are not specifically mentioned as occurring with the particular drug under investigation.

#### **7.1.4 Serious**

An Unanticipated Problem or Protocol Deviation is serious if it meets the definition of a Serious Adverse Event or if it compromises the safety, welfare or rights of subjects or others.

#### **7.1.5 Serious Adverse Event**

An adverse event or suspected adverse reaction is considered serious if in the view of the investigator or the sponsor, it results in any of the following:

- Death
- A life-threatening adverse drug experience
- Inpatient hospitalization or prolongation of existing hospitalization
- Persistent or significant incapacity or substantial disruption of the ability to conduct normal life functions
- A congenital anomaly/birth defect.
- Important medical events that may not result in death, be life-threatening, or require hospitalization may be considered a serious adverse drug experience when, based upon

appropriate medical judgment, they may jeopardize the patient or subject and may require medical or surgical intervention to prevent one of the outcomes listed in this definition.

#### **7.1.6 Disability**

A substantial disruption of a person's ability to conduct normal life functions.

#### **7.1.7 Life-threatening adverse drug experience**

Any adverse event or suspected adverse reaction that places the patient or subject, in the view of the investigator or sponsor, at immediate risk of death from the reaction as it occurred, i.e., it does not include a reaction that had it occurred in a more severe form, might have caused death.

#### **7.1.8 Protocol Deviation (NIH Definition)**

Any change, divergence, or departure from the IRB-approved research protocol.

